10.7.3 Expectedness of Events

Expectedness of all AEs will be determined according to the Investigator's Brochure as determined by Ocular Therapeutix, Inc.

10.8 Pre-scheduled or elective Procedures or Routinely Scheduled Treatments

A pre-scheduled or elective procedure or routinely scheduled treatment will not be allowed during the study period.

10.9 Procedures for Handling Special Situations

10.9.1 Pregnancy

Females should not become pregnant during the study period. If this occurs the subject should notify the Investigator immediately. The Investigator must report the pregnancy as outlined in Section 10.5. In addition, the Investigator or study site staff must report the outcome of the pregnancy to the pharmacovigilance team.

10.9.2 Unmasking for Medical Emergencies

In the case of a medical emergency or occurrence of an SAE, the randomization code may be unmasked and made available to the Investigator, Sponsor, and/or other study personnel involved in the conduct of

the study. In the absence of medical need, the randomization code will not be available to the above individuals until after the study is completed and the database is locked.

In the event of a medical need, the Investigator will treat each subject, as medically required. If the Investigator feels it is necessary to unmask a subject's treatment assignment after an emergency situation, the Investigator may call the Medical Monitor and notify the Sponsor. The treatment assignment will be revealed on a subject-by-subject basis with the approval of the Medical Monitor and Sponsor, thus leaving the masking of the remaining subjects intact. Ocular Therapeutix will make the final determination if the unmasking request will be granted. Once the unmasking request is granted the investigator or designee should use the IRT system to unmask the subject's randomization code. The investigator must also indicate in source documents and in the eCRF that the mask was broken and provide the date, time, and reason for breaking the mask. Any AE or SAE associated with breaking the mask must be recorded and reported as specified in this protocol.

Subjects will have the IP removed (Appendix 15) immediately if treatment assignment is unmasked.

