6.3 Randomization and Blinding

Cohort 1 will be open-label and treatment assignment will be known to the sponsor, investigator and subjects. All 5 enrolled subjects in Cohort 1 will receive OTX-CSI Formulation 2A.

Cohort 2 will be randomized to treatment assignment and double-masked. If unmasking is required, the integrity of the study assessments and objectives will be maintained by limiting access to the unmasked data to the two individuals in the Safety Review Group (Sponsor Medical Monitor and Sponsor Statistician) who are not involved in the study conduct or directly by the investigator if required in an emergency.

A randomization schedule will be computer-generated by a qualified biostatistician independent of the study conduct or project team and uploaded into the EDC system. The EDC/IRT system will be used for randomization and unmasking.

The HV and OTX-CSI inserts administered to subjects at randomization in the double-masked treatment phase will be comparable in appearance. Study subjects and investigators and their staff will be masked to the identity of treatment until the final database is locked. The Sponsor's personnel involved with the conduct and monitoring of the study will remain masked until completion of the study and database lock.

Appropriate precautions must be taken to prevent unauthorized access to the randomization scheme. Unless the subject's safety requires otherwise and if time permits, the decision to unmask a treatment assignment is to be made jointly by the Investigator and Sponsor's medical monitor.

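### Protocol 10.9.2, the emergency unmasking section, puts the code break behind sponsor approval and does not carry over the direct investigator access granted in Protocol 6.3

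*Protocol*

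**What the plan says.** Protocol 10.9.2 (Unmasking for Medical Emergencies) opens by allowing the code to be broken and made available to the investigator, among others, in a medical emergency or when an SAE occurs. On care it says: "In the event of a medical need, the Investigator will treat each subject, as medically required". The procedure then runs as follows:

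- How a request begins: if the investigator thinks it necessary to learn the "treatment assignment after an emergency situation, the Investigator may call the Medical Monitor and notify the Sponsor".
- Who approves it: "The treatment assignment will be revealed on a subject-by-subject basis with the approval of the Medical Monitor and Sponsor", so that other subjects stay masked.
- Who has the last word: "Ocular Therapeutix will make the final determination if the unmasking request will be granted".
- When the code is broken: "Once the unmasking request is granted the investigator or designee should use the IRT system", and then records the break with its date, time and reason.
- What happens to the insert: "Subjects will have the IP removed (Appendix 15) immediately if treatment assignment is unmasked".

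Protocol 6.3 (Randomization and Blinding) limits access to unmasked data to two Safety Review Group members, "or directly by the investigator if required in an emergency". It also says: "Unless the subject's safety requires otherwise and if time permits, the decision to unmask a treatment assignment is to be made jointly". The two parties to that joint decision are the sponsor's medical monitor and the investigator. SAP 2.4 repeats both statements.

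The Safety Review Group charter (Protocol Appendix 2), where it deals with unmasked review of Cohort 2 data, sends the reader to 10.9.2 for unmasking procedures. It does not mention 6.3.

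**The concern.** Two sections of one protocol describe how a masked assignment is revealed when a subject is in trouble, and they differ on whether the investigator must wait for permission. The section whose title names emergencies is the one with the approval steps. The section that allows direct access deals with randomization and blinding in general.

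A site looking for the emergency procedure is likely to turn to 10.9.2. Read alone, it sends the site to the Medical Monitor and sponsor and lets it use the IRT only after the request is granted. What is at stake is a possible delay or refusal of a code break that 6.3 would have let the investigator make at once. This is a matter of site procedure and subject safety; it does not affect the analysis.

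**Working it through.** No arithmetic applies. The check sets the provisions side by side and asks whether 10.9.2 contains, or points to, an emergency route without approval.

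| Question | Protocol 10.9.2 | Protocol 6.3 (and SAP 2.4) |
|---|---|---|
| Situation addressed | Medical emergency or SAE | Unmasking in general, with an emergency clause |
| May the code be broken in an emergency? | Yes | Yes |
| Must someone approve first? | Yes, Medical Monitor and Sponsor; the sponsor decides finally | Not where the investigator needs direct access in an emergency |
| Stated exception for urgency or safety? | None | Yes, both subject safety and lack of time |
| Reference to the other section? | None | None |

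1. **Does the opening sentence of 10.9.2 supply the direct route?** It says the code may be broken and made available to the investigator. It does not say that the investigator may do this unaided. The later sentences name who approves and who decides.

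2. **Do the approval sentences carry an exception?** No. None of the three (approval, final determination, IRT use after the grant) mentions urgency, safety or time.

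3. **Can the approval sentences be confined to later requests?** The wording allows it. The trigger is a wish to unmask after an emergency situation, the contact is permissive (the investigator may call), and the request in the final-determination sentence could be that later request. On this reading 6.3 governs the acute case. But 10.9.2 does not state the division. If it is the intended one, the section titled for emergencies gives no steps for unmasking during the emergency itself. The instruction to document date, time and reason is in 10.9.2, after the grant.

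4. **Does SAP precedence settle it?** SAP 5 says the SAP supersedes the protocol where they differ, and SAP 2.4 agrees with 6.3. That clause sits under changes to planned analyses. It does not set site procedure, and a site handling an emergency works from the protocol.

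5. **What would a delay cost?** Under 10.9.2 the investigator treats as needed without waiting for the code. Under 7.6 the insert can be removed at any time for any reason. After unmasking it is removed, with no distinction by arm. Treatment and removal therefore do not depend on the code. No endpoint, population or estimate depends on which unmasking rule applies.

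**The case against.** The strongest reply is that the protocol has to be read as a whole. Section 6.3 already grants direct emergency access, SAP 2.4 repeats it, and Protocol 13.1 requires investigators to follow the whole document. Reading the approval sentences of 10.9.2 as covering requests made after the event is natural, and on that reading nothing conflicts; only a cross-reference is missing. The documents also name no emergency in which knowing the arm would change management. Protocol 4.5 puts immediate release of all the cyclosporine from both inserts at 750-fold below the daily oral maintenance dose.

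Much of this stands. The protocol does contain an emergency route, and the consequence is small. Protocol 4.4 lists severe angioedema and dyspnea among post-approval reactions to topical cyclosporine, so an investigator could want the code, but nothing in the documents shows that it would alter acute care.

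The reply does not remove the gap. The harmonizing reading has to be inferred, and the section a site would open first states the restrictive steps without limiting them. An emergency procedure should not depend on the reader finding a clause elsewhere and working out that it overrides.

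A reader might go further and infer that the protocol forbids investigators to unmask in an emergency, or that the sponsor holds a veto over every emergency code break. The documents do not support that: 6.3 and SAP 2.4 say otherwise, and the wording of 10.9.2 can be read as limited to later requests.

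**Conclusion.** The point holds as an unresolved inconsistency in the emergency unmasking procedure. Section 10.9.2 makes IRT unmasking follow sponsor-side approval and neither repeats nor refers to the direct access in 6.3 and SAP 2.4. A site relying on 10.9.2 alone could have a code break delayed or refused.

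The practical risk is small and there is no effect on any estimate. The documents give no rate of emergency code breaks, and none is assumed. They also do not give the IRT permissions, so delay is a possibility and has not been demonstrated. It would be wrong to infer that subjects would go untreated while approval is sought, because 10.9.2 has the investigator treat as required regardless. The correction is worth making because it is cheap and brings the emergency section into line with access the protocol already grants.

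**What to change.** Amend Protocol 10.9.2 as follows:

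- State that in a medical emergency the investigator may unmask the subject directly through the IRT without prior approval.
- Require prompt notification of the Medical Monitor and sponsor afterwards, and documentation of the date, time and reason (10.9.2 already requires that documentation for an approved break).
- Limit the approval and final-determination sentences to non-urgent requests.
- Add a cross-reference to 6.3.

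Confirm that IRT permissions let investigators break the code in this way. No SAP change is needed, since SAP 2.4 already agrees with 6.3.

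The cost is a few sentences, one cross-reference and a permissions check. The downside is slightly less sponsor control over code breaks, which 6.3 already concedes in emergencies.

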10.9.3 Regulatory Reporting

Suspected Unexpected Serious Adverse Reactions (SUSARs) are SAEs that are unexpected and judged by the Investigator or Ocular Therapeutix to be associated to the study treatment administered. Ocular Therapeutix will report SUSARs to the appropriate authorities within the required regulatory timeframes. Reports of SUSARs will be made to IRBs, and Investigators, as needed.

11 STATISTICAL METHODS AND DATA ANALYSIS

11.1 Statistical Methods

Summaries for continuous variables will include the sample size, mean, standard deviation, median, minimum, and maximum. Summaries for discrete variables will include frequencies and percentages. The baseline visit will be defined as the last non-missing measure prior to initiation of investigational treatment. Differences between treatment groups will be calculated as OTX-CSI minus HV and change from baseline will be calculated as follow-up visit minus baseline visit values.

11.2 Unit of Analysis

Both eyes will be treated with the same treatment/formulation. If both eyes qualify, the eye having the higher total corneal fluorescein staining score will be designated as the study eye and the other eye designated as the non-study eye. If both eyes have the same total corneal fluorescein staining score, the study eye will be determined by the biostatistician prior to the analysis and will be detailed in the Statistical Analysis Plan. If only one eye qualifies, that eye will be the study eye, but both eyes will still receive the same treatment/formulation.

The unit of analysis in this study will be the primary study eye for all efficacy summaries. Efficacy summaries will be presented for the primary study eye for Cohort 2 only. Cohort 1 will be included for all safety summaries and will include summaries of the secondary study eye. Additional analyses may be presented for the secondary study eye. All summaries will be presented by treatment group and visit, where appropriate. In addition to looking at the individual formulations, the two formulations of OTX-CSI and HV will be combined and summarized.

11.3 Sample Size Determination

No formal sample size calculations were performed. The proposed sample size will allow for initial estimates of efficacy as well as provide for sufficient safety information to be obtained, while still limiting the number of subjects exposed to the IP.

11.4 Statistical Significance

All statistical testing will be done at the two-sided alpha level of 0.05. As this is a Phase 1/2 study, no adjustments to alpha will be made for testing of multiple endpoints.

11.5 Trial Termination

Should it become apparent during the trial that there is a significant safety concern or there is an issue with enrollment, the trial may be terminated. In addition, should information become known during the course of the trial that would negatively impact the trial, the trial may be terminated. In addition, the FDA or another regulatory authority may terminate the trial.

11.6 Missing Data

The primary analyses of efficacy data will use Markov Chain Monte Carlo (MCMC) multiple imputation methodology to impute missing data. Sensitivity analyses, to determine robustness of results, will be performed using last observation carried forward (LOCF) and observed data only.

11.7 Efficacy Analyses

The primary efficacy endpoint analysis of Schirmer Test will use a linear model with fixed effects of baseline Schirmer Test value and treatment will be used to compare Schirmer Test change from baseline and absolute values with least square means comparing OTX-CSI treatment groups to HV treatment groups at each visit. In addition to looking at the individual formulations, the two formulations of OTX-CSI and HV will be combined and a linear model, two-sample t-test and Wilcoxon rank sum test will be performed at each visit.

Secondary efficacy endpoint analyses of Total Corneal Fluorescein Staining (tCFS) using NEI scale, CFS sub-regions using NEI scale, Conjunctival Lissamine Green Staining using NEI scale, Eye Dryness Score (VAS) and Ocular Surface Disease Index questionnaire (total score, each of the three domains and the individual questions) will be analyzed similar to the Schirmer Test. Speed measures (overall score and individual questions) will also be analyzed similarly, however only change from baseline will be presented. Percent of subjects with ≥ 10 mm increase in Schirmer at Week 12 will be analyzed using a chi-squared test.

11.8 Exploratory Analyses

Tear Film Break Up Time at Week 12 will be analyzed similar to the Schirmer Test, however only observed data will be used. Presence of insert, ease of insertion as assessed by the Investigator and ease of visualization as assessed by the Investigator at all post-baseline visits will be summarized using discrete statistics and will be tested between treatment groups (all treatment groups separately and combined) using the Pearson chi-squared statistic.

11.9 Reporting Deviations

Should there be changes in any analyses described in the protocol, the statistical analysis plan will document them. Should there be changes in any analyses described in the statistical analysis plan, the final clinical study report will describe them.

11.10 Subject Population(s) for Analysis

Intent-to-Treat (**ITT**): The ITT population will include all randomized subjects. Analysis on the ITT population will be used as the primary efficacy analysis and will be performed for all efficacy endpoints, analyzing subjects under the treatment to which they were randomized.

Per Protocol (PP): The PP population will include all ITT subjects who do not deviate from the protocol in any way likely to seriously affect the efficacy outcomes of the study. Analysis on the PP population will be used as secondary efficacy analysis and will be performed for select efficacy endpoints, analyzing subjects under the treatment actually received. Important protocol deviations will be identified prior to locking the study database.

Safety: The Safety population will include all subjects who received IP (OTX-CSI or HV). Analyses performed on the Safety population will be according to the treatment the subject actually received.

12 STUDY MANAGEMENT AND DATA COLLECTION

12.1 Confidentiality

All trial subject data collected and processed for the purposes of this trial should be maintained by the investigator and his/her staff with adequate precautions as to ensure that the confidentiality of the data is in accordance with local, state, and federal laws and regulations.

Monitors, auditors, and other authorized representatives of CRO, drug safety, the sponsor, the IRB/IEC approving this trial, the FDA, the Department of Health and Human Services, other domestic government agencies, and other foreign regulatory agencies will be granted direct access to the trial subject's original medical and trial records for verification of the data and/or clinical trial procedures. Access to this information will be permitted to the aforementioned individuals to the extent permitted by law.

A report of the results of this trial may be published or sent to the appropriate health authorities in any country in which the IP may ultimately be marketed, but the subject's identity will not be disclosed in these documents.

12.2 Source Documents

Source documents may include a subject's medical records, hospital charts, clinic charts, the investigator's trial subject files, as well as the results of diagnostic tests such as X-rays, laboratory tests, and EKGs. The investigator's electronic copy of the eCRFs serves as the investigator's record of a subject's trial-related data.

12.3 Case Report Forms

All subject data will be captured in the subject source documents which will be transcribed to the eCRFs. The investigator is responsible for ensuring that trial data is completely and accurately recorded on each subject's eCRF, source documents, and all trial-related materials. All trial data should also be attributable, legible, contemporaneous, original, accurate and complete. Recorded data should only be corrected in a manner that does not obliterate, destroy, or render illegible the previous entry (e.g., by drawing a single line through the incorrect entry and writing the revision next to the corrected data). An individual who has corrected a data entry should make clear who made the correction and when, by adding to the correction his/her initials as well as the date of the correction.

Data entry of all enrolled and randomized subjects will use software that conforms to 21 CFR Part 11 requirements and will be performed only by staff that have been trained on the system and have access

to the system. Minimal data will be entered for screen failure subjects. An audit trail will be maintained within the electronic system to capture all changes made within the eCRF database. After the end of the trial and database lock, compact discs (CDs) containing copies of all applicable subjects' eCRFs will be provided to each investigator site to be maintained on file by the investigator.

12.4 Records Retention

All trial related correspondence, subject records, consent forms, record of the distribution and use of all IP and copies of case report forms should be maintained on file for at least two years after the last approval of a marketing application in an ICH region and until there are no pending or contemplated marketing applications in an ICH region; or until at least two years have elapsed since the formal discontinuation of clinical development of the IP. These documents will be retained for a longer period if required by the applicable regulatory requirements or by an agreement with the sponsor. It is the responsibility of the sponsor to inform the investigator/institution as to when these documents no longer need to be retained. The investigator must notify the sponsor prior to destroying trial documentation even after the above-mentioned time has passed.

If the responsible investigator retires, relocates, or for other reasons withdraws from the responsibility of keeping trial records, custody must be transferred to a person who will accept the responsibility. The sponsor must be notified in writing of the name and address of the new custodian.

13 STUDY MONITORING, AUDITING, AND INSPECTING

13.1 Study Monitoring Plan

Each investigator must adhere to the protocol as detailed in this document and agrees that any changes to the protocol must be approved by Ocular Therapeutix, Inc., prior to seeking approval from the IRB/Ethics Committee. Investigators' proficiency in observing and scoring ophthalmic observations will be established and documented via review of academic training and experience, prior to examining subjects. Each investigator will be responsible for enrolling only those subjects who have met protocol eligibility criteria. During study conduct, Ocular Therapeutix, Inc and/or its representative will conduct periodic monitoring visits to ensure that the protocol and Good Clinical Practice (GCP) are being followed. The monitors may review source documents to confirm that the data recorded on the electronic case report forms (eCRFs) are accurate. Further details of the trial monitoring (including medical monitoring) will be outlined in a monitoring plan.

The investigator and institution will allow Ocular Therapeutix, Inc., monitors or its representatives and appropriate regulatory authorities direct access to source documents and CRFs to perform this verification. Data Managers will also review data and may interact with site personnel for clarifications.

It is important that the investigator(s) and their relevant personnel are available during the monitoring visits and possible audits or inspections and that sufficient time is devoted to the process.

